3.4 Outcomes

Figure 2. MUSA Outcomes

3.4.1 Detailed Description of Primary Study Outcome

The primary outcome for this study is the mean change from baseline in UDI-total score at 6 months after the intervention is administered (mid-urethral sling or Botox A). Outcomes at 6 months will assess the effectiveness of the study treatments.

We have elected to use the total UDI as the primary outcome because it is a validated, condition-specific patient-reported outcome (PRO) measure. A PRO is a measurement of any aspect of a patient's health status that comes directly from the patient (without interpretation by the physician, researcher, other). In clinical trials, symptom indices and quality of life PRO instruments are increasingly being used as primary outcomes and supported by federal agencies.^{69,70}

The long form of the UDI is a 19 item, validated UI symptom specific PRO measure with 3 subscales: stress, irritative, and obstructive symptoms.¹ The UDI fulfills the minimum qualities needed for interpretation in a clinical trial including construct, criterion and discriminant validity. Construct validity (convergent) was originally established by demonstrating significant correlation between the overall UDI and its subscale scores with the number of IEs on 7-day diary and pad tests. Criterion validity was established by correlating total and subscale scores with physician diagnoses. The UDI can effectively discriminate between known UI clinical groups and diagnoses (specifically genuine SUI, urodynamic detrusor overactivity, or mixed) and is responsive to change. Higher scores represent more severe disease or bother from the patient perspective.

The UDI will be the primary outcome because it has all the characteristics that are important for a MUI population:

1. It captures a meaningful outcome from the patient perspective, incorporating both the presence and bother of SUI and OAB symptoms.
2. The overall UDI score includes both a stress and irritative subscale, allowing us to comprehensively capture both SUI and OAB symptom outcomes.
3. It includes 3 UI items that are not necessarily specific to stress or urgency and thus can help capture UI episodes for which patients cannot clearly distinguish as SUI or UUI.
4. It can capture both improvement and worsening of preexisting symptoms, but also the development of new urinary symptoms.⁵⁶

Another important advantage of using the UDI as a primary outcome measure is that its minimum important difference (MID) has been extensively studied. From the patient perspective, MID represents “the smallest difference in score in the domain of interest which patients perceive as beneficial...”²⁸ Statistically, *the minimum important difference (MID) of a measure is a score change that reflects a clinically meaningful response to treatment and represents the “between group” criterion that needs to be met or exceeded in order for study results to be considered clinically meaningful*. From the clinical trial perspective, the MID represents the magnitude of benefit for which trials should be powered to minimize type 1 and type 2 errors.

Table 6 shows the MID of the UDI from three large clinical trials. Prior estimates of the MID for the UDI were obtained in urge-predominant and stress-predominant MUI populations by Dyer et al and Barber et al respectively. The most recent estimate of MID of the UDI is from the ESTEEM trial which recruited subjects that are most similar to the MUSA population: women with MUI who have bothersome stress and bothersome urgency incontinence. The baseline mean UDI score of ESTEEM is higher than that of the BE-

DRI and ATLAS populations. Using the anchor-based method, ESTEEM recommends a MID of -26 for the UDI total, -10.2 for the UDI-irritative subscale, and -5.4 for the UDI-stress subscale.

Table 6: UDI MID

Trial / Author	Population	Endpoint / Intervention	UDI Component	Anchor-Based MID	Distribution-Based MID (1/2 SD)	Recommend MID	SD
ESTEEM	MUI Baseline mean UDI Score: 178 ± 43 , UDI-irritative 66 ± 20 , UDI stress 86 ± 18	Sling vs. Sling + Behavioral at 3, 6, 12 months	UDI-total	-26.1		-26	43 (at bl) 55 (change) 46 (chg model)
			UDI-irritative	-10.2		-10	20 (at bl) 25 (change) 21 (chg model)
			UDI-stress	-5.4		-5.4	18 (at bl) 28 (change) 23 (chg model)
BE-DRI, Dyer 2011 ⁷¹	Pure urge/Urgo-predominant MUI.	8 month Meds +/- BPTx	UDI-total	-45 to -35	-25	-35	50
	Baseline mean UDI score 120 ± 49 , UDI irritative 58 ± 22		UDI-irritative	-20 to -15	-11	-15	26
ATLAS, Barber 2009 ¹⁰	Pure SUI/SUI predominant MUI	3 month Pessary vs BPTx vs both	UDI-total	-22.6 to -6.4	-21.9 to -18.8	-11	36
	Baseline mean UDI score 80 ± 40 , UDI stress 47 ± 19		UDI-stress	-16.5 to -4.6	-10.6 to -9.1	-8	21

There are at least 3 different ways to analyze the UDI scores:

- #1. Compare postoperative *mean UDI scores* between groups at 3 and 6 months
- #2. Compare *mean changes* (delta) in UDI scores from baseline to 3 and 6 months between groups (*preferred, see below*)
- #3. Dichotomize “success” and “failure” as women who achieved a 26-point improvement versus those who did not (also known as “responder analysis”)

For analysis, we plan to compare *mean changes* (delta) in UDI scores from baseline to 3 and 6 months between groups (option #2). We prefer this to comparing postoperative mean UDI scores between groups (option #1) because 1) it will account for baseline differences in UDI scores between groups, which will be important in the unlikely event that baseline scores between groups differ in spite of randomization and 2) UDI scores typically have a distribution that is highly skewed, but differences from baseline are more likely to be normally distributed. We have elected to not dichotomize patients into responders and non-responders based on MID because information such as “slightly improved” is typically lost when lumping subjects into groups and furthermore, patients may worsen significantly on one of the subscales and yet be classified as a “success”.

3.4.1.a Advantages of the UDI Over Other Outcome Measures

The team discussed using bladder diary, IIQ (Incontinence Impact Questionnaire), and global impression of severity or improvement. Arguments against each of these were based on the following rationale:

1. Problems with using bladder diary as primary outcome:

- a. Diary does not capture a meaningful patient outcome- It is becoming increasingly clear that typical clinical trial endpoints such as reduction in the number of incontinence episodes (IEs), voided volumes, etc. do not capture what is meaningful to patients. For example, having 3 large urinary urgency leaks a day may be more bothersome than having 20 small stress leaks or having 20 urgency associated voids may be more bothersome than having 1 UUI episode. Diary IEs also have limited correlation with patient satisfaction.⁷² Finally, bladder diaries have been shown to be less reliable in women with MUI, particularly for the SUI component.⁷³
- b. Diary cutoffs to define improvement for MUI are unknown-What percent improvement for the SUI component and for the UUI component is clinically important for a woman with MUI? Any cutoffs chosen would be arbitrary.
- c. Using IEs on bladder diary as a primary outcome would require a minimum number of IEs (approximately 3-4 IE/3days) at baseline to be able to detect a change. The protocol team felt that setting such strict inclusion criteria would be too limiting to allow recruitment of a good range of MUI severity (see Inclusion Criteria, Section 4.2).

For all of these reasons, the team decided against using bladder diary IEs as the primary outcome and to instead focus on measures that can capture outcomes from the patient perspective. However, IEs on the bladder diary will be a secondary outcome because this outcome measure has been widely used in other urinary incontinence trials.

2. Problems with using a quality of life measure as primary outcome

The protocol committee had extensive discussion about using a quality of life measure, such as the Incontinence Impact Questionnaire (IIQ) as the primary outcome. The IIQ long form measures the impact of UI on the QOL and is therefore suitable for capturing the effect of treatment of either stress or urgency component on QOL.¹ Ultimately, the team decided to not use the IIQ as a primary outcome because the IIQ does not allow measurement of the impact of the interventions individually on the stress and urgency components. Though there are some women with MUI who may not be able to clearly distinguish all UI episodes as stress- or urge- related, the team felt it would be important to capture the effect of the interventions individually on symptoms. Finally, the MID of the IIQ was determined in stress-predominant and urge-predominant populations and has less validity for a MUI population.^{10,71}

3. Problems with using global impression measure as primary outcome

3.4.1.c Management of Subjects Who Request Other Non-Study Treatment for SUI and/or OAB After Botox A or Mid-Urethral Sling

The overarching goal of MUSA is to evaluate the effect of Botox A or mid-urethral sling on improving both SUI and UUI outcomes in women with MUI. Therefore, other non-study treatment for urinary incontinence (either SUI or UUI) should not be offered during the 6 month study period. We anticipate that the number of patients who request treatments other than Botox A or mid-urethral sling will be low (See section *Management of patient who are unwilling for randomization or request treatment off-protocol*). Patients requesting other non-study treatment during the 6-month study period will be asked to take advantage of treatments offered per-protocol and defer other treatments until after 6 months. Any non-study treatment will be recorded as a protocol deviation.

3.4.2 Secondary Outcomes

The UDI total score at 3 months is a secondary outcome. Because MUI includes both SUI and UUI, it is important to be able to report SUI, UUI and other OAB symptom outcomes separately. The UDI-stress

subscale and UDI-irritative subscale will be important secondary outcomes for which MUSA will be powered to detect differences and each will have a priori analysis plans (see Section 6, Statistical Considerations).

3.4.2.a Urgency Urinary Incontinence/Overactive Bladder Symptom Outcomes

Unlike ESTEEM, “desire for surgical treatment of SUI” is not an inclusion criterion for MUSA and there is an objective UUI inclusion criteria of ≥ 4 UUIEs on a 3 day diary. Therefore, it is likely that the MUSA population may have more prominent UUI symptoms than ESTEEM. A potential important clinical problem in this population is the potential for persistent or worsening OAB symptoms after mid-urethral sling, it is highly important to capture and report on the cardinal symptoms of OAB (urgency, frequency, urgency urinary incontinence and nocturia) from the patient perspective. The UDI-irritative subscale measures symptom burden, impact, and changes related to OAB which are important aspects that cannot be directly observed or otherwise measured. It is highly responsive to treatment-related change and is able to discriminate among levels of change in all bladder diary variables (urinary urgency, frequency and urge incontinence) and patient ratings of treatment benefit. Particularly for MUSA, this comprehensive OAB measure will be important to understanding how mid-urethral sling may affect all OAB symptoms individually and as a whole.

3.4.2.b Stress Urinary Incontinence Symptom Outcomes

Botox A has been shown to reduce overall UIEs in a urge-predominant MUI population (see section 2.4). Additionally, the common presence of cough-induced DO suggest that Botox A could potentially improve SUI symptoms in patients with MUI. However, direct data on whether Botox A can improve SUI symptoms are lacking. Therefore, it is important that SUI outcomes are reported separately in MUSA.

Prior studies have also reported higher failure rates for SUI in women with MUI. In ESTEEM, improvement in stress score of the UDI was greater in the combined sling-BPTx group than the sling only group though these differences were not statistically significant (-67.11 vs – 61.65, $p = .08$). The MUSA population is different from ESTEEM in that they will already have “failed” behavioral therapy. Therefore, they may be at higher risk for persistent SUI symptoms. Other studies have also reported higher failure rates for SUI for women with MUI undergoing sling surgery. One study by Paick et al evaluated 274 women, of which 73 had MUI and reported cure rates for SUI to be 78% for the MUI group and 95% for the pure SUI group.²³ They also reported that low maximal urethral pressure at baseline was associated with a greater risk of persistent OAB, suggesting the possibility that profound urethral dysfunction may contribute to persistent symptoms. In ESTEEM, baseline urodynamic evaluation (UDE) parameters that predicted failure included detrusor overactivity, lower volume at first urge, and Valsalva leak point pressure < 60 cmH₂O. A study by Gleason et al using data from the University of Alabama at Birmingham including 534 women with MUS found that a lower proportion of women with MUI had SUI success compared with the SUI only group (64% vs 84.5%, $p < 0.001$).⁷⁴ Therefore, as a secondary outcome, we will also compare SUI outcomes between women randomized to Botox A versus mid-urethral sling. SUI symptoms will be measured using the UDI-stress subscale.

3.4.3 ***Other Outcomes***

3.4.3.a **Other UUI/OAB Outcomes**

1. Bladder diary – Change in IE frequency and type, number of urgency incontinence episodes, urgency incontinence severity with voids, number of diurnal voids, and number of nocturnal voids will be assessed and compared between groups at 3 and 6 months.
2. Overactive Bladder treatment satisfaction (OAB-SAT-q)⁷⁵ The OAB-SAT-q is an 11 item instrument designed to assess patient satisfaction with treatment in a clinical setting. There are three 3-item subscales (Satisfaction, Side Effects, Endorsement) and two single items (Convenience, Preference). Response options are presented on 4-, 5-, and 6-point Likert scales. It has demonstrated good psychometric properties in OAB/UUI patients receiving treatment. We will compare OAB-SAT-q scores at 3 and 6 months between treatment groups.
3. Overactive Bladder Questionnaire- subscales (OAB-q) – The OAB-q is a validated, responsive questionnaire that includes 8 symptom bother items (SS) and 25 health related quality of life (HRQOL) items of 4 subscales (coping, concern, sleep, and social interaction).⁷⁶ In a systematic review of UI questionnaires by Avery et al, the OAB-q was rated as “grade A”, highest recommendation specifically for OAB symptoms.⁷⁷ Each item is rated on a 6-point Likert scale ranging from “not at all bothered” to “a very great deal bothered” for symptom items and “none of the time” to “all of the time” for HRQOL items. Subscales are summed and transformed into scores ranging from 0-100 with higher bother scores indicating increasing symptom bother and higher HRQOL scores indicating better quality of life.^{78,79} We will compare change from baseline in OAB-q subscale scores at 3 and 6 months between treatment groups.

3.4.3.b **Quality of Life/Global Impression**

We will compare change from baseline score in the measures below at 3 and 6 months between treatment groups.

1. Incontinence Impact Questionnaire Long Form (IIQ-LF)⁵⁷
2. Pelvic Organ Prolapse/Urinary Incontinence Sexual Questionnaire (PISQ-IR)⁸⁰
3. European Quality of Life-5 Dimensions (EQ-5D)⁸⁴
4. Short Form 36 (SF-36)⁸¹ and Short Form 6D (SG-6D)⁸²
5. Patient Global Impression of Improvement (PGI-I) and Patient Global Impression of Severity (PGI-S).⁸³ Observed PGI-I at 3 and 6 months will be compared between groups.

3.4.3.c **Safety/Additional Treatment**

1. Additional re-treatments for SUI or UUI within 6 months of treatment, and type of re-treatment
2. Return to OR for sling revision due to worsened OAB symptoms, urinary retention, mesh exposure, repeat sling
3. Rate of urinary retention, UTIs and recurrent UTIs
4. Rate of other serious and non-serious adverse events.

3.4.3.d Cost-Effectiveness Outcomes

The cost-effectiveness analysis will be conducted from the health care sector and societal perspectives and will be expressed as incremental cost required to produce one additional unit of quality-adjusted life year (QALY). Data on each subject's use of medical and non-medical resources, related to urinary incontinence will be collected during the follow up period. Direct and indirect costs of the treatment of urinary incontinence with Botox A compared to mid-urethral sling (MUS) and women's preference for health states for improvement in urinary incontinence will be estimated.

We plan to capture incremental direct health care, direct non-medical, and indirect resource use related to study interventions and complications and other urinary incontinence management (such as other UI treatment, UI products and management of side effects). Costs will be estimated using the resource costing method. Direct medical service use collected from each study case report form and direct non-medical and indirect costs collected from patient questionnaires are monetized by multiplying the number of units of each resource use by the average unit cost of this item in dollars. Detailed individual cost data will not be collected. This method allows a consistent capture of resource use when costs are incurred across multiple health systems or payers. Detailed case report forms, that include the interventions performed (e.g. mid-urethral sling surgery and Botox injections) and clinical events (e.g. complications and additional treatment) will be completed by the study coordinator at study visits. Patient questionnaire on direct non-medical costs (e.g. pads, laundry) and indirect costs (e.g. time, lost productivity) will be completed at study visits 2 weeks and 6 months. Data from medical resource types (physician visits, medications, hospital admissions and emergency room visits) will be collected. Cost for each direct medical service use, direct non-medical items, and indirect items will be assigned based on national Medicare reimbursement rates or other standardized national unit costs as indicated in the following **Table 8**.

Table 8: Resource Utilization Data Collection and Price Data Source by Utilization Category

Service	Source Documentation	Price Weight
Surgery: mid-urethral sling	Case Report Form	Medicare reimbursement
Botox injection	Case Report Form	Medicare reimbursement
Medication	Case Report Form	Drug Red Book
Physician visit	Case Report Form	Medicare reimbursement
Complication: surgery	Case Report Form	Medicare reimbursement
Complication: hospitalization	Case Report Form	Medicare reimbursement
Complication: ER visit	Case Report Form	Medicare reimbursement
CIC products	Case Report Form	Average national cost
UI products	Questionnaire	Average national cost
UI laundry / dry cleaning	Questionnaire	Average national cost
Time	Questionnaire	Average national cost
Lost Productivity	Questionnaire	Average national cost

Rationale for Using the EQ-5D and SF-6D to Measure Utility Values

The European Quality of Life-5 Dimensions (EQ-5D) (EuroQol Group, <http://www.euroqol.org>), preference-based utility index algorithm will be used to calculate each subject's utility score.⁸⁴ This instrument will be collected at baseline and follow up study visits (3 months and 6 months). The EQ-5D has 5 attributes (mobility, self-care, usual activities, pain/discomfort and anxiety/depression) with 3 levels each for a possible 243 unique health states. The EQ-5D scoring function is based on the time-tradeoff method with UK Scores ranging from -0.59 to 1.00 and US Scores from -0.11 to 1.00. This instrument has been previously validated in women with urinary incontinence and used in women with urinary incontinence, including ESTEEM.^{41,42,62,63} These data will be used to compare change in QALYs between the two treatment groups. We are choosing to use a general scale to calculate change in utilities (rather than condition-specific) to allow for comparison of cost-effectiveness results with other interventions and diseases.

The Short Form 6-Dimensions (SF-6D) is a single summary preference based or utility measure of health derived from 11 items of the SF36 and will also be used to calculate each subjects utility score.^{81,82} This instrument will be collected at baseline and follow up study visits (3 months and 6 months). The SF-6D has 6 dimensions (physical functioning, role limitation, social functioning, pain, mental health, vitality); each dimension has 2 to 6 levels for 18,000 possible unique health states. The SF-6D scoring function is based on the standard gamble method. The SF-6D preference-based measure is a continuous outcome scored on a 0.29 to 1.00 scale, with 1.00 indicating "full health. This instrument has been previously validated and used in women with urinary incontinence and pelvic organ prolapse.⁸⁵⁻⁸⁷ We are using both the SF-6D and the EQ-5D to measure utility scores because though both the SF-6D and EQ-5D weigh health states on a scale of 0 (dead) to 1 (optimal health) and the MID values for both instruments are similar, they are not directly comparable. Studies have demonstrated that the SF-6D does not appear to describe health states at the lower end of the scale as well as the EQ-5D but is better able to describe health states and detect improvements towards the top of the utility scale.⁸⁸

Further data is needed to determine which instrument performs better as a preference-based utility and general HRQOL measure for women with MUI or if both are acceptable.

A questionnaire to measure direct non-medical costs (e.g. pads, laundry) and indirect costs (e.g. time, lost productivity) will be administered. Based on similar questionnaires used in SISTER,⁸⁹ Value⁹⁰ and ESTEEM⁴⁹ studies, this instrument should take approximately 15 minutes for a subject to complete at 3 months and 6 months.

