2.5 Rationale for Considering Mid-Urethral Slings for the Treatment of MUI in Women

“Traditional teaching” is that women with MUI should not undergo anti-incontinence surgery for SUI due to the potential risk of worsening OAB symptoms. However, these recommendations are based on expert opinion and secondary analysis and retrospective studies that included traditional bladder neck slings and colposuspensions.⁴⁴⁻⁴⁶ Most studies report that success rates of the treatment of the SUI component in a MUI population are as high as 80%.^{47,48} Increasing evidence also indicates that 1) the rate of de novo UUI after mid-urethral slings is low and that 2) mid-urethral slings improve UUI and OAB symptoms in women with MUI (**Table 2**).

The recently completed ESTEEM trial was conducted in women with MUI who at baseline had 1) “moderately or severely bothersome” SUI and UUI; 2) at least one documented stress and urgency incontinence episode on the 3-day bladder diary and 3) desired surgical treatment of SUI.⁴⁹ In ESTEEM, 480 women with MUI were randomized to sling alone or sling combined with BPTx. Women in both groups had improvements in MUI symptoms as measured by the UDI-total score at 12 months (-128.15 vs -114.73, p =.03) but the difference (-13.42) did not reach the pre-specified MID of 35 points indicating that combined therapy was not more effective than MUS alone for treating MUI. However, both groups had mean within-group changes in the UDI-total, UDI-irritative, and UDI-stress scores that exceeded the corresponding MIDs of 35 points (SD 50.4), 15 points (SD 25.6) and 8 points (SD 21.5) respectively.¹⁰ Women in both groups also reported reduction in total UI, UUI, and SUI episodes on bladder diary with significantly greater improvements in the total and urgency incontinence episodes in the combined treatment group. OAB-q symptom severity and satisfaction scores also improved in both groups and were not significantly different between groups. Finally, the rate of new or worsening urgency incontinence at or beyond the 3-month visit was 4.5% in the combined and 2% in the MUS only group. Taken together, these findings demonstrate that **mid-urethral sling alone improves overall symptoms of MUI including both the stress and urgency components and is associated with a low overall rate of worsening of de novo UUI/OAB.**

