6. STATISTICAL CONSIDERATIONS

6.1 Sample size and Power

MUSA will randomize 146 women to treatment with Botox or Sling in a 1:1 ratio. The sample size was derived to provide sufficient power for the primary Aim (comparison of Botox versus sling after 6 months) assessed for the primary outcome (change in UDI total score).

6.1.1 *Primary Aim*

Assumptions

For the primary outcome (UDI total score change from baseline at 6 months), alpha was set at 0.05 and power was set at 90%.

Sample size estimates were based on an evaluation of minimum important differences (MIDs) and corresponding standard deviation (SD) for the UDI total score from the ESTEEM study of MUI, with support from other published populations of women with urge and stress incontinence; however, the populations on which those MIDs were based might differ from the target population of mixed incontinence for MUSA. Thus, our goal was to power the study to detect a statistically significant difference between groups in change from baseline in UDI total score at 6 months for the UDI MID determined from ESTEEM as that will be a clinically important difference in our population. **Table 6** summarizes the published MIDs for ESTEEM, BE-DRI, and ATLAS. To use the most accurate standard deviation applicable to MUSA, we calculated the SD based on a mixed effects repeated measures model with adjustment for baseline UDI score and clinical site rather than the SD of the observed data in order to account for improvements in variance estimation from the covariate adjustment planned for MUSA. To most closely match MUSA, this analysis model included all 3-month and 6-month ESTEEM data points after any retreatments and excludes patients with <4 Urge IEs/3 days. The MID for ESTEEM UDI-Total is 26, and the SD=46.5 from the analysis model, resulting in an effect size = 0.56.

Total number of randomized patients required to meet planned power estimates were adjusted for the assumed patient discontinuation rate at 6 months. ROSETTA and ESTEEM discontinuation rates are displayed in **Table 10**. Based on average estimates from ROSETTA and ESTEEM, we plan for 5% discontinuation rate by 6 months.

Table 10: 6 Month Discontinuation Rates from ROSETTA and ESTEEM

Study	Population	6-Month Discontinuation Rate
ROSETTA	UUI	10/386=2.6%
ESTEEM sling arm	MUI	16/235 = 6.8%
Plan for MUSA	MUI	5%

Sample Size and Power Calculation

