Sample size estimates were generated using nQuery Advisor under the assumptions outlined above. The evaluable sample size required at 6 months for 90% power for the primary total UDI outcome is 69 per arm. Because data from ROSETTA and ESTEEM suggests that follow-up at 6 months should be about 95%, a total sample size of 73 randomized per treatment arm is selected ($69/0.95 = 73$), for a total sample size of 146 randomized participants. These calculations are provided in **Table 11**.

Table 11: MUSA Power Calculation for N=146 (73 Per Treatment Arm)

UDI component	Primary or Secondary Outcome	MID	SD ^a	Effect Size	Alpha	Power at 6 months	Randomized Sample Size per Group ^b
UDI-Total	Primary	26 (ESTEEM)	46.5	0.56	0.05	90%	73
UDI-Total	Primary	26 (ESTEEM)	46.5	0.56	0.05	85%	62
UDI-Total	Primary	26 (ESTEEM)	46.5	0.56	0.05	80%	55
UDI-Total	Primary	23	46.5	0.50	0.05	82%	73

^a SD: standard deviation is estimated from ESTEEM participants with at least 4 Urge IEs/3 days using a repeated measures linear model for change from baseline to 3 and 6 months with adjustment for baseline value and clinical site.

^b Assumes 5% of randomized participants discontinue by 6 months estimated by average of ROSETTA and ESTEEM

Sensitivity to MID Assumptions for the Primary Outcome

With the sample size of 146 subjects and the planned standard deviation, our study will have 82% power to detect a statistically significant difference in UDI-total score at $p<0.05$ if the true difference is as small as 23 points (0.50 effect size) between groups at 6 months (**Table 11**). Thus, the planned sample size may allow for analyses to assess whether the true MID in this population is smaller than 26.

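### Protocol 3.4.2 says the trial is powered for UDI-stress, but Section 6 gives power for UDI-total only, and the protocol's own inputs give about 28% for UDI-stress

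*Protocol*

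**What the plan says.** Protocol 3.4.2 states that the UDI-stress "subscale and UDI-irritative subscale will be important secondary outcomes for which MUSA will be powered to detect differences", and refers to Section 6 for the plans.

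Section 6.1 covers less than that: "The sample size was derived to provide sufficient power for the primary Aim", assessed on change in UDI-total. It continues: "The evaluable sample size required at 6 months for 90% power for the primary total UDI outcome is 69 per arm". All four rows of Table 11 are for UDI-total, as are the rows of Table 2 in the 12-month addendum. SAP Section 6 also gives power for UDI-total only. Protocol 6.2.2 gives the subscales an analysis and an alpha of 0.05, but no power and no target difference.

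Protocol 3.4.1 sets the standard for a target difference: "the MID represents the magnitude of benefit for which trials should be powered to minimize type 1 and type 2 errors". The values follow in the same section: "ESTEEM recommends a MID of -26 for the UDI total, -10.2 for the UDI-irritative subscale, and -5.4 for the UDI-stress subscale". For UDI-stress, Table 6 lists SDs of 18 (baseline), 28 (raw change) and 23 (change model). Protocol 2.5 cites older values for total, irritative and stress in turn: "the corresponding MIDs of 35 points (SD 50.4), 15 points (SD 25.6) and 8 points (SD 21.5) respectively".

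**The concern.** The reader is told that the trial is powered for UDI-stress and is sent to a section with no such calculation. The UDI-stress MID is also small relative to its SD. For UDI-total the ratio is 26/46.5 = 0.56. For UDI-stress it is 5.4/23 = 0.23, less than half as large, so a sample sized for the first cannot give similar power for the second.

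UDI-stress is the outcome that shows whether Botox A gives up stress benefit relative to the sling. Someone who believes the trial is powered for it could take a non-significant result to mean no important difference, which this sample size would not support.

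**Working it through.** **Inputs**
- 69 evaluable per arm; 73 randomized per arm with 5% discontinuation (Protocol 6.1.1).
- Alpha 0.05, two-sided, for the primary and, unadjusted, for each secondary outcome (SAP 7.8).
- UDI-total: MID 26, change-model SD 46.5 (Protocol 6.1.1).
- UDI-stress: MID 5.4, change-model SD 23, raw change SD 28 (Protocol 3.4.1, Table 6).
- UDI-irritative: MID 10 to 10.2, change-model SD 21, raw change SD 25 (same table).
- Older UDI-stress MID: 8 points, with SD 21 (Table 6) or 21.5 (Protocol 2.5).

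**Method.** Two-sample t-test with n = 69 per arm and 136 degrees of freedom. The noncentrality is δ / (SD × √(2/n)), where √(2/69) = 0.1703, and the critical value is t(0.975, 136) = 1.978. Power comes from the noncentral t distribution.

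**Reproducing the plan's figures (UDI-total)**
- 26 points: 26 / (46.5 × 0.1703) = 3.28, power 90.3%. The smallest n giving 90% is 69 per arm, and 69/0.95 rounds up to 73.
- 23 points: 23 / (46.5 × 0.1703) = 2.90, power 82.2%.

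Both agree with Table 11, so this is in effect the plan's method.

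**The same method for the subscales**

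| Outcome | Difference | SD | Effect size | Power |
|---|---|---|---|---|
| UDI-stress | 5.4 | 23 (change model) | 0.23 | 27.8% |
| UDI-stress | 5.4 | 28 (raw change) | 0.19 | 20.3% |
| UDI-stress, older MID | 8 | 21 | 0.38 | 60.3% |
| UDI-stress, older MID | 8 | 21.5 | 0.37 | 58.3% |
| UDI-irritative | 10 | 21 (change model) | 0.48 | 79.3% |
| UDI-irritative | 10.2 | 21 (change model) | 0.49 | 80.9% |
| UDI-irritative | 10 | 25 (raw change) | 0.40 | 64.5% |

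For the first row the noncentrality is 5.4 / (23 × 0.1703) = 1.38, below the critical value of 1.98. Even the baseline SD of 18, the smallest printed for UDI-stress, gives only 42% at 5.4 points.

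**Detectable difference.** The effect size detectable with 80% power is 0.480. For UDI-stress that is 0.480 × 23 = 11.0 points, or 0.480 × 28 = 13.5 points with the slightly unrounded multiplier (0.4804). For 80% power at 5.4 points the SD would have to be 5.4/0.480 = 11.2, about half of 23.

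**Precision.** The expected 95% CI half-width is 1.978 × SD × 0.1703, which is 7.7 points with SD 23 and 9.4 points with SD 28. Both exceed 5.4, so an observed difference of exactly zero would still leave an MID-sized difference in either direction inside the interval.

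**A comparison within the protocol.** Protocol 3.4.2.b reports ESTEEM UDI-stress changes of -67.11 and -61.65 with p = .08. That gap of 67.11 − 61.65 = 5.46 points, almost exactly the MID, did not reach significance in a trial that randomized 480 women. The treatments compared were different, so this is only an illustration.

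**The case against.** The strongest reply is that being powered to detect differences names no size, and that the real stress difference between a sling and a bladder injection may be far larger than the MID. Protocol Table 7 gives a 6-month UDI-stress change of -64 in the ESTEEM sling-only arm. If Botox A lost one fifth of that (0.2 × 64 = 12.8 points), power would be about 90% with SD 23, or 76% with SD 28. This stands as far as it goes: the low power applies to differences near the MID, and large losses would probably be detected. It does not support the sentence. The MID is the only criterion for a target difference that the protocol gives, no larger UDI-stress target is stated, and Protocol 3.4.2.b says direct data on Botox A and stress symptoms are lacking.

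Some milder points also stand. SAP 7.8 calls the secondary p-values descriptive, the SAP does not repeat the power claim, and estimates with 95% CIs are already planned. Neither document says that a non-significant UDI-stress result will be read as no difference. The documents print no wrong power figure for UDI-stress; the fault is a claim without support. Section 6 gives no power for UDI-irritative either, and the figure of about 80% depends on the change-model SD. These points limit the consequences but do not make the UDI-stress claim true.

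**Conclusion.** The concern holds. The design does not have the power that Protocol 3.4.2 claims for UDI-stress, judged by the protocol's own standard. At the ESTEEM MID power is about 28%, so a true difference of that size would be missed about 7 times in 10. The older 8-point MID, with the SDs printed for it, gives only 58–60%.

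Two assumptions matter. The first is that the MID is the intended target, as Protocol 3.4.1 says. The second is that the Table 6 SD of 23 applies to women with at least 4 urgency episodes in 3 days, because an SD for that subset is given only for UDI-total. There the two figures hardly differ (46 in Table 6, 46.5 in Table 11), and rounding of the 23 moves power only between 27% and 29%.

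The error is confined to UDI-stress. UDI-irritative, at about 79–81% with the change-model SD, is conventionally adequate, since the 90% target is set only for the primary outcome. The primary outcome and its sample size are not affected.

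**What to change.** In Protocol 3.4.2, delete the power claim for UDI-stress or replace the sentence with the actual figures, for example:

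> The trial is sized on UDI-total. With 69 evaluable women per arm, power at the ESTEEM MID is about 80% for UDI-irritative (10 points, SD 21) and about 28% for UDI-stress (5.4 points, SD 23). The UDI-stress difference detectable with 80% power is about 11 points. A non-significant UDI-stress result will be read from its 95% CI against the MID, and not as evidence of no important difference.

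Add a UDI-irritative row and a UDI-stress row to Table 11, labelled secondary. If a stress difference larger than the MID was intended, state it there with its justification.

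The minimum repair is to remove the clause; the last sentence of the example is a useful safeguard for readers. The cost is one sentence and two table rows, with no extra participants and no change to the planned model. What is given up is a more favourable stated property for UDI-stress.
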